**Study-Day 3 (2 weeks after Study Day 2)(~8 hours):**

- 1. PE testing battery
- 2. Single session **Active** iTBS+ APT or **Placebo** iTBS+APT
- 3. Alternate ImE test (MDS or AMPS) three times at 30min intervals
- 4. PE testing battery
- 5. Suitability ratings 1-3

**Study-Day 4 (2 weeks after Study-Day 3) (~2.5 hours):**

[figure not shown]
- 1. PE testing battery
- 2. Suitability rating 1-8

**Optional Study for Participants with diagnosis of TBI only- Day 5 (to occur within 2 weeks of Day 4, can occur on same day as Day 4) (~2 hours)**

- 1. Single session of Active iTBS at GIMME site of stimulation
- 2. ImE test: MDS, one time only
- 3. ImE test: AMPS, one time only

### Figure 3. Study Procedures by Study-Days 1 thru 4

ImE = Immediate Effects Tests; s-AMPS = Streamlined AMPS or MDS = Modified Digit Span; PE = Persisting Effects Tests for all participants

**Interventions.** All iTBS sessions will be **double-blinded**, but APT exercises **will not be blinded**. For **Active** iTBS and **Placebo** iTBS, the left DLPFC using the Resting Network Mapping algorithm.

**fMRI (neuroimaging)-** Functional MRI (fMRI) measures will be collected at Baseline. The fMRI measures will include structural imaging, 20 minutes of resting-state fMRI, diffusion tensor imaging (DTI) and an Arterial Spin Labelling Sequence (ASL). Participants will be in the MRI for approximately 55 minutes. fMRI scanning, for all participants, will take place at Northwestern University's CTI in the Olsen Pavilion located at [name].

Veterans will be responsible for transportation to the CTI, however parking vouchers will be provided at no cost to the participant. Parking is available at the Northwestern Memorial Hospital parking garage located across from the Olsen Pavilion. Research staff will be present on day of scan and available to provide assistance.

Scanning will take place on a Siemens Prisma 3.0 T MRI scanner equipped with a 64-channel head/neck coil. A high-resolution 3D MP-RAGE T1-weighted sagittal anatomical scan (voxel size = 0.8 mm isotropic resolution; 224 sagittal slices) will be collected for each participant. Resting state BOLD data will be collected using T2\* weighted EPI with a TR=0.5s, TE=25ms, flip angle of 48°, and 2mm isotropic voxels and a multiband factor of 8. Rest data will be collected while the subject views a fixation crosshair. The DTI data will use a two shell (64 directions per shell) acquisition with diffusion values of 1000 mm^2/sec. The acquisition will collect 1.5mm isotropic voxels with a TR=4500, TE=62ms and a multiband factor of 4, and 96 slices.

The collection of the fMRI data will be directed by [name]. fMRI data collected at CTI will be de-identified and uploaded to Northwestern University Research Image Processing System (NURIPS), an online collaborative research environment for securely storing, managing, analyzing and sharing de-identified medical imaging, associated data (e.g., behavioral), and results from advanced customizable processing pipelines. NURIPS is supported by both Northwestern University IT and Feinberg School of Medicine IT and takes advantage of the NU high performance computing cluster, Quest. NURIPS is a secure environment that supports the latest NU policy and procedures for encryption of data during transit and rest, provides granular project level access controls with varying permissions based on user groups, and allows non-NU collaborators access once they obtain an affiliate NetID. All data are backed up and have restore points that go back for 30 days. Once the data is uploaded to NURIPS, a copy will be

downloaded onto Hines VA secure research servers for storage on \\v12.med.va.gov\\v12\\hin.

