Aligned with VA RR&D's mission to create knowledge and innovations advancing the rehabilitative health and care of Veterans, this project will scale-up the scientific basis for developing and, ultimately, delivering Veteran-tailored, interventions that improve the aspects of function identified by Veterans across neurologic diagnoses as important to their well-being. For Veterans with moderately impaired levels of cognition who are struggling with daily life, thereby requiring assistance with complex instrumental activities of daily living, this project will explicate critical and practical barriers to developing Veteran-tailored interventions that optimize cognitive function in daily life. The results will be used to design and conduct future merit research examining the over-arching hypothesis that restorative cognitive interventions developed according to transdiagnostic sampling and matched with a biotype algorithm, compared to a diagnosis-based algorithm, result in better functional performance of Veteran-valued IADL.

With additional supplemental funds awarded through the Infinite Hero Foundation administered through Northwestern University Feinberg School of Medicine Department of Physical Medicine and Rehabilitation, two additional aims have been added to this study. With the provide funds, the study will enable all Veteran participants enrolled in the Pilot study to have their baseline fMRI to be collected at Northwestern University Clinical Translational Imaging (NU CTI) center located at Olson Pavilion at [name].

Secondly, it will provide additional optional treatment for up to 12 enrolled Veterans with a diagnosis of Traumatic Brain Injury who have enrolled and completed the main study. Participants with the diagnosis of Stroke will not be eligible to participate in the Optional Experimental Treatment sessions.

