**Study-Day 2 (4 days after Study Day 1)(~8 hours):**

- 1. PE testing battery
- 2. A single session of **Active** iTBS or **Placebo** iTBS
- 3. Randomly assigned ImE test (MDS or AMPS), administered 3-times at 30 min intervals, each interval includes 5 to 15 min of rest).
- 4. PE testing battery
- 5. Suitability ratings 1-3

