We will use each Veteran's MT, an indicator of cortical excitability, as the benchmark for determining iTBS intensity for each participant ( iTBS intensity will be 80% of each subject's RMT). This intensity will be maintained throughout study participation.

**iTBS** will be delivered with the Magventure MagProX100 with MagOption stimulator and Cool Coil B65. Active iTBS will be provided using active setting (A) at 80% of each Veteran's resting motor threshold. Placebo iTBS participants will not receive any stimulation as the coil will be switched to placebo (P) setting. To maintain double-blind in A and P settings, Veterans and researchers wear headphones connected to a sham noise generator.

For **APT**: 30 min of training exercises, 10 min metacognitive training, and 5 min of functional goal setting. Study-Days 2 or 3 sessions will each include novel exercises. For metacognitive training, the Veteran will be instructed on how to use strategies to self-regulate or to "think about his or her own thinking" and to self-monitor while performing an activity and efficiently allocate his or her cognitive resources. Goals will then be set to implement the strategy in the Veteran's daily life.

**iTBS** will be delivered with the Magventure MagProX100 with MagOption stimulator and Cool Coil B65. Active iTBS will be provided using active setting (A) at 80% of each Veteran's resting motor threshold. Participants randomized to active iTBS will receive stimulation at the left DLPFC at 80% RMT. 80% RMT is the intensity most commonly used and cited in the literature and has been shown to be safe. The right DLPFC will be marked in the TMS Localite

Navigation system for each participant. The navigation system will provide target guidance and will help the researcher to position the coil very precisely in reference to the participant's brain. The neuronavigation system will be used every iTBS session to ensure reproducibility and consistency at the stimulation site.

For the Optional Study: The site of stimulation will be determined by the GIMME modeling. Optimal brain target is identified through GIMME modeling, which is a directed functional connectivity modeling approach based on iterative model optimization.

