Since we seek to identify one ROI as the optimal iTBS GIMME target and as each pathway is comprised of two ROIs, we will select one of the two ROIs comprising the pathway selected as the most important to cognitive function. This ROI is the ROI with the highest total degree. The graph theory metric of total degree quantifies the sum of in-degree (number of connections coming into the ROI) and out degree (outbound connections). As both in and out degree reflect importance of the ROI to cognition, we will use total degree to select the optimal brain region. If the total degree between the brain regions is equal, we will base the decision on TMS accessibility, Gray Matter Density and/or structural integrity.

Regarding testing Aim 4, the results from above GIMME modeling and decision criteria will, ultimately, test hypothesis that, within our study population of persons **with** moderate cognitive impairment from TBI, there are sub-types/sub-groups of persons with common brain circuitry important to cognition.

Past GIMME work indicates that a minimum of 7 persons with moderate cognitive impairment from TBI will be sufficient to identify an optimal group-level model as well as sub-types/subgroups. That is, 7 participants per diagnosis, here moderate cognitive impairment from TBI, has consistently identified an optimal group-level model as well as subgroups within this diagnosis. Thus, we will strive to enroll at least 7 participants into these optional studies.

**AIM 5:** Determine immediate gains in working memory and performance of complex IADL after provision of a single session of iTBS targeting to the same location in the L DLPFC after a single session of iTBS targeting the optimal GIMME brain target. We hypothesize that average gains in working memory and functional performance after a single iTBS session site will be

significantly different according to site of stimulation (GIMME site). For each iTBS session, we will compute pre and post iTBS MDS and AMPS scores to be used to compute change in working memory and functional performance of IADL. For each outcome and each treatment site, the mean change will be computed. Using student t-tests, we will compare mean change in working memory and mean change in functional performance between the L DLPFC vs GIMME sites. This will allow us to examine the concept that treatment sites personalized by ROI structure is or is not important for optimizing clinical benefits of iTBS.

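### As scheduled, Aim 5's comparison of stimulation sites is fully aliased with session order, and the double-blind statement is not supported for Day 5

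*Combined protocol and SAP*

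**What the plan says.** - **Day 5 content** (5.1 Study Design, optional study): "Single session of Active iTBS at GIMME site of stimulation", then MDS once and AMPS once. No placebo session and no L DLPFC session is listed.
- **Day 5 position**: "to occur within 2 weeks of Day 4, can occur on same day as Day 4". Section 3.0 Objectives offers the optional treatment to TBI Veterans "who have enrolled and completed the main study".
- **Comparator**: the main study stimulates the left DLPFC. Study-Day 2 gives "A single session of Active iTBS or Placebo iTBS", followed by one of MDS or AMPS, three times. Study-Day 3 adds APT to the assigned iTBS and uses the other test.
- **Blinding** (5.1, Interventions): "All iTBS sessions will be double-blinded". The mechanism, given under Motor Threshold Testing & Brain Mapping, is "To maintain double-blind in A and P settings, Veterans and researchers wear headphones connected to a sham noise generator".
- **Analysis** (5.6, Aim 5): Student t-tests of mean change, L DLPFC against GIMME, with no term for period, order, form or earlier treatment. The stated inference is "This will allow us to examine the concept that treatment sites personalized by ROI structure is or is not important for optimizing clinical benefits".
- **Practice effects** (5.6, Aim 2): if detected, the adjusted re-analysis covers 2i and 2ii only.
- **Other descriptions of the optional study**: 3.0 and 5.3 speak of optional treatment sessions in the plural, and Aim 5 in 3.0 and 5.6 mentions a session at the same L DLPFC location.

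**The concern.** A site comparison needs site to vary separately from when the session occurs. On the printed schedule it does not: every GIMME result comes from the last session and every L DLPFC result from an earlier one. The plan itself expects persisting and cumulative treatment effects (Aim 2ii) and treats practice effects on MDS and AMPS as an open question (Aim 2iii). Either could produce a Day 5 difference with no site effect at all, or hide a real one. Because Aim 5 is meant to inform whether personalised targeting matters, a shift due to order could be credited to site and carried into later work.

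The blinding statement adds to this. Its wording makes no exception for Day 5, but the only mask described hides whether the coil is in the active or placebo setting, and on Day 5 that setting never varies.

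**Working it through.** **1. The plan's own figure.** The main-study size reproduces: effect size 0.90, 80% power, two-sided 5% (level assumed) gives 20.39, so 21 per group and 42 in total; 42 / 0.88 = 47.7, so 48. It does not bear on Aim 5, for which no power is stated. The minimum of 7 is justified only for GIMME model recovery.

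**2. What is aliased.** Write the expected change at an L DLPFC session as m + s_L + p_early, and on Day 5 as m + s_G + p_5. Here s is the site effect and p collects everything attached to the session: order, practice, test form and carry-over.

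Day 5 minus L DLPFC = (s_G − s_L) + (p_5 − p_early)

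There is one observable contrast and two unknowns. A column for session in the model would be identical to the column for site, so adding a period term cannot help. If s_G = s_L, the expected estimate is p_5 − p_early, whatever the sample size.

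**3. What p contains by Day 5, from the schedule.**
- Stimulation: two assigned iTBS sessions, the second with APT.
- AMPS: 1 at screening + 5 in the persisting-effects battery + 3 as the immediate-effects test = 9 earlier administrations. A Veteran assigned AMPS on Day 2 has had 1 + 1 = 2 before the first post-iTBS test.
- MDS: 3 earlier administrations. Section 5.5 gives the forms in one identical order to everyone, so form is tied to session as well.
- Change score: Aim 5 needs pre and post scores for each session, but Day 5 lists MDS and AMPS once each, both after iTBS. A pre value taken from an earlier visit would bring practice and elapsed time into the change itself.

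**4. What randomised order would do.** With GIMME second the expected difference is d + p; with GIMME first it is d − p; their average is d. In a simulation of 40,000 runs with no site effect, no carry-over and session shifts of 0 to 0.8 SD, bias stayed within 0.003 SD and the 5% test rejected in 4.8% to 5.1% of runs (n = 6 and 12).

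**5. How many same-person pairs exist.** There are 24 TBI Veterans. Equal allocation implies 12 Active, and an equal split of the Day 2 test implies 12 / 2 = 6 with Active iTBS alone on a given immediate-effects outcome. Optional-study eligibility does not require Active assignment. If opting in is unrelated to arm, the expected number is 12 × 6/24 = 3 among 12 opt-ins, or 7 × 6/24 = 1.75 among 7. AMPS is also in the battery before and after Day 2 treatment, so using those scores would raise its ceiling to 12. The battery's post score follows the three immediate-effects tests, and the plan does not say which AMPS score Aim 5 uses.

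**6. Illustration only.** Assume a paired two-sided 5% test, no site effect, and a session shift of 0.2, 0.3 or 0.5 SD of the paired difference (noncentrality = shift × √n). At n = 6 a site difference is declared in 6.9%, 9.3% or 17.1% of trials; at n = 3, in 5.6%, 6.2% or 8.4%. The rates are low only because so few pairs have little power; the bias is the full shift in each case.

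**7. Blinding.** The blinding sentence covers every session; the mechanism covers the A/P settings; Day 5 is always A. No masking of site, which is the contrast that Aim 5 tests, is described.

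**The case against.** **Unblinding is not documented.** A reader might infer that Veterans and testers know the Day 5 condition, so that Day 5 is open-label. No section says so. The fixed setting and the optional procedures in the consent make it plausible, but site could be masked without the plan saying it. What stands is narrower: the documents do not support a double-blind for Day 5.

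**The blinding sentence may concern the main study only.** It follows a figure caption limited to Study-Days 1 to 4 and is followed by text on the left DLPFC. That is a fair reading, and a reason to state the scope.

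**A second optional session may have been intended.** The plural wording in 3.0 and 5.3, and the same-location session in Aim 5, leave this open. A reader should not conclude that a repeat L DLPFC session is ruled out. None is scheduled, however, and no site order is given.

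**The aim is exploratory and the wording modest.** Section 3.0 labels it exploratory, and 5.6 speaks of examining a concept, so it would be too strong to say that the plan promises proof. Even so, the hypothesis is of a significant difference by site, and the inference is stated both ways.

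**Safeguards exist.** There are six MDS forms, AMPS tasks are never repeated, at least two weeks separate Day 3 from Day 5, and within-session change would remove stable gains. These may shrink the session shift but do not separate it from site, and the last depends on a Day 5 pre score that is not listed.

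**Larger false-positive rates are tempting.** Calculating them at the full 12 or 7 opt-ins presumes that many same-person Active iTBS-alone pairs, which the Day 2 immediate-effects tests do not supply. The plan also does not say that its t-tests are paired.

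**Conclusion.** The point holds for the schedule as printed. Site is completely aliased with session order, test exposure, MDS form and any carry-over, and the practice-effect adjustment does not reach Aim 5. This follows from the schedule and needs no assumed effect size. The bias equals the session shift; its size and direction are unknown, and the rates in the illustration rest on assumed shifts and pairing. The ceiling of about 6 pairs per outcome assumes equal allocation and the Day 2 immediate-effects tests.

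The double-blind statement is unsupported for Day 5, but the documents do not establish that anyone is unblinded to site. If the sponsor did intend a second optional session, the aliasing would depend on how the order of sites is set, which is nowhere stated. The aim is exploratory and small, so this is a correction the plan should make; it does not threaten the main study.

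**What to change.** 1. **Blinding (5.1):** limit the double-blind statement to Study-Days 2 and 3. For Day 5, state that the setting is fixed as Active and whether site is masked from Veterans and from testers.
2. **Schedule:** reconcile the plural optional sessions in 3.0 and 5.3, and the same-location L DLPFC session in Aim 5 (3.0 and 5.6), with the single Day 5 session in 5.1.
3. **Aim 5 (5.6):** if Day 5 stays as scheduled, replace the stated inference. Report the contrast as an exploratory estimate, with a confidence interval, of the combined effect of site and session order (and of any unmasked delivery). Make no claim that personalised sites are or are not important. Such a claim would need a design in which site order is randomised.

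If Day 5 stays as scheduled, the cost is wording only, with no added session. The downside is that the exploratory aim claims less.

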**Figure 1. Four Step Screening Process: Summary of Exclusion Criteria by Steps**

For this within-subject placebo-controlled partially-blinded treatment protocol (Fig 2), we will enroll 48 medically stable Veterans with stabilized recovery trajectories after a stroke or a TBI and who have a homogeneous level of moderately impaired cognitive function persisting after standard rehabilitation.

An equal number of Veterans with stroke/TBI (24-stroke; 24-TBI) will be enrolled, but we will over-sample females (Figure 2). For each iTBS group to include an equal number of Veterans with stroke/TBI, Veterans will be randomly assigned by diagnostic groups, to receive Active iTBS or Placebo iTBS. To measure immediate effects (ImE), an equal number of Veterans with stroke/TBI within each iTBS group will be randomly assigned to be tested with the Modified Digit Span (MDS) or AMPS, three times at 30 min intervals. Persisting effects (PE) tests will be administered to all participants at five timepoints including prior to and after Active iTBS or Placebo iTBS and 2-weeks later prior to the 2nd intervention, where all Veterans receive APT paired with their assigned iTBS (Active iTBS + APT or Placebo iTBS + APT). The alternate ImE test is then administered three times at 30 min intervals, followed by re-administration of all PE tests. Two weeks later, all PE tests are administered a 5th time (B4). ImE and PE measures are used to define magnitude and duration of cognitive change. Randomization (SAS Proc Plan) will be managed by one un-blinded researcher who will not provide interventions or conduct testing.

**Figure 2. Study Design (ImE = Immediate Effects Tests; AMPS = AMPS or MDS = Modified Digit Span; PE = Persisting Effects Tests for all participants; Study Day-1: Obtain Covariates and Treatment preparation information; B0 = Pre-Study-Day-2; B1 = Post-Study-Day-2; After 2-Weeks B2 = Pre-Study-Day-3; B3 = Post-Study-Day-3; After 2-Weeks B4 = Study-Day 4)**

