**Rules for Pausing treatment to Evaluate Need to Change iTBS Treatment Protocol:**

- 1) Any seizure
- 2) Skin break-down on scalp at site of TMS
- 3) Constant headaches that do not resolve with acetaminophen
- 4) Suicidality response on C-SSRS is 2 or higher
- 5) A composite score of visuomotor processing speed assessments that falls below 2 standard deviations from the mean.

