  - RRT arrives within 5-10 minutes of seizure onset and assumes responsibility for carrying out all emergency procedures. Research team will notify RRT of intervention and patient's vital signs thus far to facilitate coordination of care. RRT initiates the tasks below; the time frame for these tasks may run into next phase.
    - O2 administration if SpO2 <90%
    - Cardiac monitoring
    - Glucose assessment
  - MD will assess the situation and prescribed benzodiazepine will be administered by RRT if indicated. Respiratory support will be provided by RRT if necessary.
- Within 20-40 minutes-Second therapy phase

- Emergency medical services continues individualized care.
- Following termination of seizure activity, medical evaluation completed by emergency room physician, [name], covering MD or on call Epilepsy physician

RRT will determine timing of transportation to ER once subject is determined to be stable for transport.

The stimulating coil will be used on multiple Veterans. To prevent the spread of contamination from one Veteran to the next, the coil will be disinfected and sanitized after every iTBS session.

To further ensure participant safety, all female Veterans will submit to a urine pregnancy screen at baseline. If the urine screen is positive for pregnancy, the Veteran will be excluded from participation.

To prevent injury during participation in AMPS assessment, all Veterans will be supervised by an AMPS certified Occupational Therapist.

*Psychological:* If the participant exhibits frustration or fatigue, then the response plan is to pause testing and comfort them. Testing will be resumed after the Veteran exhibits signs of reduced frustration. Should the Veteran experience PTSD symptom trigger during any treatment or testing, the response plan will be to immediately consult with the Hines Mental Health Service and follow their recommendation.

*To monitor depression*, specifically suicide ideation, the C-SSRS will be administered at baseline and repeated as part of each battery assessment. Administration of the C-SSRS will be as defined:

- At each C-SSRS administration, all participants will complete the first two questions, #1 'wish to be dead' and # 2 non-specific active suicidal thoughts'
- For participants answering questions 1 and 2 affirmatively, then researchers will administer the entire C-SSRS and

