For measuring immediate changes in cognitive function, we will use the aforementioned **AMPS**. For each of the *three administrations, in 30-min intervals*, a unique task will be randomly selected (without replacement) from the set of tasks developed during Step 4 (Fig 1). Thus, the same IADL is never repeated for the same Veteran.

**Persisting Effects (PE) Measures.** This battery includes the same five tests/sub-tests administered during screening (Fig 1, Step-4: AMPS, RBANS, WAIS-IV Digit Span, DKEFS subtests and BRIEF-A). As the BRIEF-A will be re-administered, the study Neuropsychologist will review BRIEF-A scores and, if there are compelling reasons, Veterans with scores suggesting atypical validity will be withdrawn. This battery also includes tests to measure change in mood: Columbia Suicide Severity Rating Scale (C-SSRS) *Beck Anxiety Inventory (BAI)*, and the *Posttraumatic Stress Disorder Checklist (PCL)*. To assess fatigue, we will use the Fatigue Severity Scale (FSS), which is a self-report measure of prior-week fatigue during nine activities and current fatigue. To measure behavioral features of agitation, we will use the *Agitated Behavioral Scale (ABS)*.

Table 2: Instrumentation: Testing Battery					
Immediate Outcome Effects (ImE)	Hrs/Admin	Aims	Variable Types	# Reps	
AMPS	1.5	1 & 2	Continuous (logit)	3	
Modified Digit Span (MDS)	0.2	1 & 2	Proportional (% correct)	3	
Persisting Effects Testing Battery (PE)	Hrs/Admin	Aims	Variable Types	# Reps	
Repeatable Battery for Assessment of Neuropsych Status (RBANS)	1.0	2	Continuous (normed score)	5	
Weschler Adult Intelligence Scale (WAIS-IV) Digit Span			Proportional (% correct)	5	
Delis-Kaplan Executive Functioning System (DKEFS): Color-Word			Continuous (normed score)	5	
Behavior Rating Inventory of Executive Function (BRIEF)			Continuous (normed score)	5	
AMPS	1.5	2	Continuous (logit)	5	
PTSD Checklist (PCL)	0.1	2 & 3	Mean # symptoms/ severity	5	
Columbia Suicide Severity Rating Scale (C-SSRS)	0.1	2 & 3	Raw score (Veteran rating)	5	
Beck Anxiety Inventory (BAI)	0.1	2 & 3	Raw score (Veteran rating)	5	
Agitated Behavior Scale (ABS)	0.1	2 & 3	Raw score (research clinician rating)	5	
Fatigue Severity Scale (FSS): Prior Week Daily Living Score	0.1	2 & 3	Raw score (Veteran rating)	5	
Fatigue Severity Scale (FSS) L VASF Current Fatigue Rating	0.1	2 & 3	Raw score (Veteran rating)	5	

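### When optional Day 5 falls on a different date from Day 4, its Active iTBS session has no same-day C-SSRS, so the suicidality rules rest on a result 1 to 14 days old

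*Combined protocol and SAP*

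**What the plan says.** **Day 5.** Section 5.1 lists three items for the optional visit. The first is "Single session of Active iTBS at GIMME site of stimulation"; the MDS and the AMPS follow, once each. The visit is "to occur within 2 weeks of Day 4, can occur on same day as Day 4". Section 3.0 offers it to up to 12 Veterans with TBI who have finished the main study, and Section 5.6 (Aim 4) aims for at least 7.

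**When the C-SSRS is given.** In Section 5.1, Protection Against Risk (psychological), "the C-SSRS will be administered at baseline and repeated as part of each battery assessment". The same paragraph adds: "At each C-SSRS administration, all participants will complete the first two questions". The full scale follows for those who answer both affirmatively. Section 5.5 says of the PE battery: "This battery also includes tests to measure change in mood: Columbia Suicide Severity Rating Scale (C-SSRS".

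**When the PE battery is given.** Section 5.1, Study Design: "Persisting effects (PE) tests will be administered to all participants at five timepoints". These are B0 to B4, the last on Study-Day 4. The lists for Study-Days 2 and 3 each begin with "PE testing battery" and place iTBS second.

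**What depends on the result.** The fourth rule for pausing iTBS is "Suicidality response on C-SSRS is 2 or higher". The C-SSRS response plan excludes a participant with active ideation (questions 3 to 5) or recent suicidal behavior and calls in the study psychiatrist.

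**The concern.** The sponsor's suicidality rules need a C-SSRS result to act on. In the main study each iTBS session follows a C-SSRS given that day. On a separately dated Day 5 the rules are still in force, since nothing exempts the optional session, but the schedule gives them no new result. A Veteran whose ideation began after Day 4 could be stimulated without being asked, although the same protocol would have asked on Day 2 or Day 3. What is at stake is a patient-safety check, not the validity of any analysis.

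**Working it through.** No power or error-rate formula applies. The check is a count of scheduled batteries and a calendar interval.

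**Step 1: reproduce the plan's count of PE timepoints.** Study-Day 2 has two (B0, B1), Study-Day 3 has two (B2, B3) and Study-Day 4 has one (B4): 2 + 2 + 1 = 5, as stated. This count describes the main study. That Day 5 has no PE battery is shown by the Day 5 list itself.

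**Step 2: compare every iTBS session.** The Day 5 window runs forward from Day 4, because only Veterans who have completed the main study may enter. Two weeks is 2 × 7 = 14 days.

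| iTBS session | C-SSRS before iTBS that day | Age of latest C-SSRS |
|---|---|---|
| Day 2 | Yes (B0) | 0 days |
| Day 3 | Yes (B2) | 0 days |
| Day 5, same date as Day 4 | Yes (B4) | 0 days |
| Day 5, separate date | None listed | 1 to 14 days |

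The third row assumes that the Day 4 battery is finished before the optional session begins, in line with the entry condition.

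**Step 3: look for another check that would ask about suicidality on Day 5.**

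- The safety indicators tracked each study day (Section 5.1, Protection Against Risk) number 12: blood pressure, heart rate, fatigue, tinnitus, sleep, dizziness, nausea, vomiting, confusion, seizure, headache and neck pain. None concerns suicidality.
- The repeat DAST on each study day concerns substance use, and only for those scoring 1 to 2.
- Stopping rule 4 is triggered by a change in mental health medication.
- The optional-study criteria in Section 5.4 contain no suicidality item.
- Section 5.7 lets the investigator withdraw a participant on safety grounds, but prompts no question.

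**Step 4: number affected.** If 7 to 12 Veterans enter, 0 are affected when every Day 5 shares a date with Day 4, and 7 to 12 when none does. The documents do not say how many will have separate dates, so the range is 0 to 12.

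**The case against.** **The Day 5 list may simply be brief.** The C-SSRS paragraph refers to each battery assessment without naming the PE battery. The Abstract calls the immediate-effects tests a testing battery, and the title of Table 2 covers both sets. Section 5.6 (Aim 5) also expects MDS and AMPS scores before and after each iTBS session, which the Day 5 list does not fully provide. So a deliberate decision to omit the C-SSRS should not be inferred. The gap still stands as written: Section 5.5 puts the C-SSRS in the PE battery, and the Day 5 immediate-effects tests come after stimulation, so a C-SSRS attached to them would be too late.

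**Two weeks is normal spacing here.** B1 to B2 and B3 to B4 are also two weeks apart, and the response plan treats the past month as the present. No sentence requires a fresh C-SSRS before every stimulation; that pattern is inferred from Days 2 and 3, where the battery also serves as an outcome measure. This is fair and keeps the point minor. But the main study does not stimulate after such an interval without first repeating the battery, and a Day 4 result cannot show later onset.

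**Stronger readings that the documents do not support.**

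- A reader might take the five C-SSRS repetitions in Table 2 as proof that none remains for Day 5. They are not. Table 2 gives the immediate-effects MDS and AMPS three repetitions each, all used by Day 3, yet both are given again on Day 5. The table does not count Day 5 procedures.
- A reader might infer that a Day 5 screen would catch any new suicidal behavior. Under the existing procedure the full scale follows only when questions 1 and 2 are endorsed, so behavior in someone who does not endorse them could still be missed.
- A reader might infer that iTBS raises suicidality risk. Potential Risks in Section 5.1 does not list it as a side effect.

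**Conclusion.** The point holds as a minor safety-scheduling gap. As written, a separately dated Day 5 is the only iTBS session with no same-day C-SSRS, and pausing rule 4 and the response plan would act on a Day 4 result 1 to 14 days old. Ideation that is new after Day 4 would not be asked about before stimulation. A positive Day 4 result would still trigger the rules.

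The reach is at most 12 Veterans with TBI, all already screened at baseline and at B0 to B4, and there is no gap when Day 5 shares a date with Day 4. No estimate, aim or error rate is affected. The conclusion rests on reading the Day 5 list literally and on Section 5.5 placing the C-SSRS in the PE battery.

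**What to change.** In Section 5.1, add as the first Day 5 item:

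> *If Day 5 is not on the same day as Day 4, administer the C-SSRS by the existing procedure (questions 1 and 2, and the full scale where that procedure calls for it) before iTBS, and apply pausing rule 4 and the C-SSRS response plan.*

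This brings the age of the latest result at that session from as much as 14 days to 0. It gives the optional session the same suicidality check as Days 2 and 3, and no more than that.

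**Cost.** One line of protocol text and about 0.1 h per Veteran (Table 2), which is 0.1 / 2 = 5% of the roughly 2 h visit. If all are separately dated, the total is 0.1 × 7 = 0.7 h for 7 Veterans and 0.1 × 12 = 1.2 h for 12. Same-day visits cost nothing extra.

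**Downside.** A positive screen may pause or cancel the session and lose that Veteran's Aim 5 data, which matters in a sample of about 7 to 12. The sponsor's rules already accept the same risk on Days 2 and 3.
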